3.2. Study Definitions and Derived Variables

3.2.1. Symptomatic Influenza Virus Infection (Shorthand: Symptomatic Infection)

Symptomatic influenza virus infection (binary yes/no) is the primary outcome for the study and will be determined by the following protocol-defined criteria, with one change from the protocol as indicated in bolded text in #1 below:

1. Viral shedding detected in NP swab(s) by qualitative **and/or quantitative** RT-PCR on at least two days beginning 24 hours after challenge until Study Day 8.
2. A cumulative symptom score ≥ 6 from daily component symptoms, including documented fever, computed across any consecutive 5-day window through Day 8 beginning on Day 2 post challenge using a modified Jackson score. Highest point score per day per sign or symptom will be used. Component signs and symptoms include fever, lymphopenia (< 1000 cells/mL), runny nose, stuffy nose, sneezing, sore throat, headache, cough, malaise, body ache, chills, feverish, shortness of breath, and earache, all ranked on a 4-point severity scale (0-3). Temperature is measured three times a day and symptoms are collected twice daily as part of the modified Jackson score.

Feverishness from the Modified Jackson Score (MJS, #2 above) and fever (graded according to Table 5) as an assessment of vital signs contribute once to the computation; the maximum of the two severity scores will be used to compute the MJS. Lymphopenia is determined based on clinical safety laboratory assessments at Days 2, 4, and 8, and graded according to Table 4.

For the purposes of determining challenge virus dose escalation during the conduct of the study, only qualitative RT-PCR results were available, and those were utilized to determine the attack rate. For the final analysis described here, quantitative RT-PCR (qRT-PCR) results will also be available, and both qualitative and quantitative RT-PCR results will be utilized for the primary analysis. As a sensitivity analysis, the attack rate will also be computed using only qualitative RT-PCR results, to compare with the primary results based on both assays. See [Section 3.2.3](#) below for how viral shedding will be determined on each study day during the challenge period.

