15. Modified Jackson Score to be obtained on the evening of Day -2 and in the morning and afternoon of each day of confinement (Approximately at 8:00 AM and after 3:00 PM) and on Day 15 during visit. Assure AM assessment on Study Day 1 is performed prechallenge.

16. Unsolicited AEs will be monitored for approximately 28 days post challenge. Review of FLU-PRO for indicators of possible severe influenza associated illness (signs, symptoms, or lab findings).

17. ECG to be performed at screening, on Study Day 6, and as clinically indicated. Sites will consult a cardiologist if ECG is abnormal to determine clinically necessary work up.

18. Among female subjects of childbearing potential, a repeat urine pregnancy test will be performed locally before CXR performed if > 7 days have passed since the negative serum pregnancy test was drawn.

19. Negative drug urine toxicology result (amphetamines, cocaine, and opiates) required on screening and (amphetamines, cocaine, opiates) on admission to the challenge unit, unless the drug is deemed acceptable by the Investigator.

20. Screening Safety/Eligibility Labs: white blood cells (WBCs), absolute lymphocyte count, hemoglobin, platelets, alanine transaminase (ALT), and creatinine (Cr).

21. Follow-Up Safety Labs: Study Days 2, 4, and 8, and as clinically indicated: white blood cells (WBCs), absolute lymphocyte count, hemoglobin, platelets, and alanine transaminase (ALT), and creatinine (Cr).

22. Including HAI, MN and NAI antibody titers on Visits 00C (Day -1) 8, 9, 10 and 11.

23. Multiplex respiratory virus assay to include SARS-CoV-2 to be performed at each site at the time points listed above. Positive results prior to influenza virus challenge will result in subject exclusion from the study. No respiratory virus testing will be done on the day of challenge. Quantitative PCR will not be done at screening.

24. If indicated.

25. If terminates study < Study Day 8 and procedure not performed on day study terminated.

Protocol 20-0005	Version 8.0
H3N2 Dose-Ranging Challenge	04May2023

26. If terminates study early and procedure not scheduled to be performed on day study terminated or if missed study procedure on scheduled day.

[figure not shown]
27. To achieve baseline data for physiological biomarkers (e.g., heartrate variability, sleep patterns, etc.).

- 28. If the Garmin and/or Oura ring is not able to be distributed at screening this will not be a protocol deviation.

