Acceptable forms of primary contraception include monogamous relationship with a vasectomized partner who has been vasectomized for 180 days or more prior to the subject receiving the influenza challenge virus, intrauterine devices, birth control pills, and injectable/implantable/insertable hormonal birth control products. Must use at least one acceptable primary form of contraception for at least 30 days prior to challenge and at least one acceptable primary form of contraception during the remainder of the study or approximately 57 days after confinement (Day -2).

**NOTE:** These criteria are applicable to female subjects in a heterosexual relationship AND of child-bearing potential. These criteria do not apply to subjects in a same sex relationship.

6. Non-habitual smoker of tobacco, e-cigarettes or marijuana

Non-habitual smokers are those who smoke no more than four cigarettes, other tobacco products, e-cigarettes (to include vaping and Juuling products) or marijuana in a week and agree not to smoke cigarettes, other tobacco products, e-cigarettes and/or marijuana products during participation in the study.

- 7. No self-reported or known history of alcoholism within the last 2 years and agrees to abstain from alcohol for at least one week before admission and throughout the confinement period
- 8. No self-reported or known history of restricted drug use for at least 30 days prior to challenge and agrees to abstain from restricted drugs throughout the confinement period
- 9. Negative drug urine toxicology result on screening (i.e., amphetamines, cocaine, and opiates) and on admission to the challenge unit (i.e., amphetamines, cocaine, and opiates)

Select drug use may be allowed at Investigator's discretion (e.g., prescribed amphetamines for ADHD).

10. Agree not to use the listed prescription or over the counter medications within 7 days prior to and through confinement period, unless approved by the investigator

Oseltamivir, zanamivir, peramivir, baloxavir marboxil, amantadine (generic) and rimantadine (Flumadine and generic), aspirin, intranasal steroids, decongestants, antihistamines, and other non-steroidal anti-inflammatory drugs (NSAIDs)

11. In good health, and do not have clinically significant medical, psychiatric, chronic or intermittent health conditions including those listed in Exclusion Criteria (Section 5.2)

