Good health, as determined by medical history, medication use and physical examination to evaluate ongoing chronic medical or psychiatric diagnoses or conditions, defined as those that have been present for at least 90 days, which would not affect the assessment of the safety of subjects or the immunogenicity of challenge. These medical diagnoses or conditions should be stable for the last 90 days (no hospitalizations, emergency room (ER) or urgent care for condition (excluding musculoskeletal conditions) and not listed in Exclusion Criteria (Section 5.2).

Subjects may be on medications only if the condition or disease is stable and not deteriorating, if the medical intervention (such as device or medication) was not available during the maximal inpatient period of time, medications are not listed in the Exclusion Criteria (Section 5.2) and pose no additional risk to subject safety or assessment of adverse events. This also includes no change in prescription medication, dose or frequency as a result of new symptoms or deterioration of the medical diagnosis or condition in the 90 days prior to enrollment. Any prescription change that is due to change of health care provider, insurance company, etc., or that is done for financial reasons, as long as in the same class of medication, will not be considered a deviation of

Protocol 20-0005	Version 8.0
H3N2 Dose-Ranging Challenge	04May2023

this inclusion criterion. Any change in prescription medication due to improvement of a disease outcome (e.g., lowering of the dosage or frequency), as determined by the site principal investigator (PI) or designated clinician licensed to make medical diagnoses and listed on Form FDA 1572, will not be considered a deviation of this inclusion criterion.

- 12. Vital signs as follows:
  - Pulse is 47 to 99 beats per minute, inclusive
  - Systolic blood pressure is 85 to 139 mmHg, inclusive
  - Diastolic blood pressure is 55 to 89 mmHg, inclusive
  - SpO2  $\geq$  95%; RR  $\leq$  18
  - Oral temperature is less than 100.6°F
- 13. Eligibility laboratory values (WBC, Absolute Lymphocyte Count, Hgb, PLTs, ALT and Cr) are within acceptable parameters

Labs within normal range or grade 1 abnormalities deemed not clinically significant by a study investigator are considered acceptable

- 14. Body mass index (BMI) >18.5 and <40 kg/m^2 at screening

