3.2.3. Infection Status

Infection status, independent of symptom status, will be defined at the participant level in two different ways:

- Participants are considered **Infected** if viral shedding is detected in NP swab(s) by qualitative and/or quantitative RT-PCR on at least two days beginning 24 hours after challenge until Study Day 8
- Participants are considered to be **Currently Infected** from their first through their last study days meeting the viral shedding definition above (and in [Section 3.2.2](#)), regardless of any intermittent negative results between those two study days.

Pre-infection and post-infection results will be determined based on the definition of Current Infection above. New-onset symptoms will be those with a maximum severity post-infection (starting on the day of first RT-PCR positivity) above that of baseline, for infected participants.

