Cumulative MJS ≥ 10 across Days 2 through 6, Days 3 through 7, or Days 4 through 8	n (%)	x (x.x)	(x.x, x.x)	x (x.x)	(x.x, x.x)	x (x.x)	(x.x, x.x)	x (x.x)	(x.x, x.x)
Symptomatic Influenza Infection: Viral shedding (by qualitative and/or quantitative RT-PCR) on at least two days and cumulative MJS ≥ 10 across Days 2 through 6, Days 3 through 7, or Days 4 through 8	n (%)	x (x.x)	(x.x, x.x)	x (x.x)	(x.x, x.x)	x (x.x)	(x.x, x.x)	x (x.x)	(x.x, x.x)
Cumulative MJS ≥ 15 across Days 2 through 6, Days 3 through 7, or Days 4 through 8	n (%)	x (x.x)	(x.x, x.x)	x (x.x)	(x.x, x.x)	x (x.x)	(x.x, x.x)	x (x.x)	(x.x, x.x)
Symptomatic Influenza Infection: Viral shedding (by qualitative and/or quantitative RT-PCR) on at least two days and cumulative MJS ≥ 15 across Days 2 through 6, Days 3 through 7, or Days 4 through 8	n (%)	x (x.x)	(x.x, x.x)	x (x.x)	(x.x, x.x)	x (x.x)	(x.x, x.x)	x (x.x)	(x.x, x.x)
Sensitivity Analysis – Varying the Number of Days of Viral Shedding									
Symptomatic Influenza Infection: Viral shedding (by qualitative and/or quantitative RT-PCR) on at least one day and cumulative MJS ≥ 6 across Days 2 through 6, Days 3 through 7, or Days 4 through 8	n (%)	x (x.x)	(x.x, x.x)	x (x.x)	(x.x, x.x)	x (x.x)	(x.x, x.x)	x (x.x)	(x.x, x.x)
Symptomatic Influenza Infection: Viral shedding (by qualitative and/or quantitative RT-PCR) on at least three days and cumulative MJS ≥ 6 across Days 2 through 6, Days 3 through 7, or Days 4 through 8	n (%)	x (x.x)	(x.x, x.x)	x (x.x)	(x.x, x.x)	x (x.x)	(x.x, x.x)	x (x.x)	(x.x, x.x)

Notes: N = Number of participants in the Safety population, n = Number of participants meeting the given criteria during the challenge period. Confidence intervals for the probability of meeting the given criteria computed via the exact Clopper-Pearson method. Confidence intervals for the mean computed via the t-distribution. MJS = Modified Jackson Score.

Table 15: Maximum Severity of Influenza Symptoms Reported During the Challenge Period by Challenge Dose Group, Safety Population

Symptom	Maximum Severity	10 ⁴ TCID ₅₀ Challenge Virus (N=X)		10 ⁵ TCID ₅₀ Challenge Virus (N=X)		10 ⁶ TCID ₅₀ Challenge Virus (N=X)		Sham Inoculum (N=X)	
		n (%)	95% CI	n (%)	95% CI	n (%)	95% CI	n (%)	95% CI
Any Symptom	Any Severity	x (x.x)	(x.x, x.x)	x (x.x)	(x.x, x.x)	x (x.x)	(x.x, x.x)	x (x.x)	(x.x, x.x)
	None	x (x.x)	-	x (x.x)	-	x (x.x)	-	x (x.x)	-
	Mild or Just Noticeable	x (x.x)	-	x (x.x)	-	x (x.x)	-	x (x.x)	-

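### The symptom half of the attack-rate definition ignores each participant's pre-challenge score; one baseline-corrected sensitivity row would show whether this matters.

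*SAP*

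**What the plan says.** SAP section 3.2.1 sets the symptom criterion as a summed score of 6 or more over the daily items, with fever among them, "computed across any consecutive 5-day window through Day 8 beginning on Day 2 post challenge using a modified Jackson score". Within each day, "Highest point score per day per sign or symptom will be used". Table 14 spells out the windows as Days 2-6, 3-7 and 4-8. Protocol section 4.1 sets the same symptom criterion. None of these places mentions a baseline score.

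Baseline scores exist. The Schedule of Activities has the MJS taken on the evening of Day -2, twice on Day -1 and on Day 1, where footnote 15 says "Assure AM assessment on Study Day 1 is performed prechallenge". I found no eligibility rule that caps the pre-challenge MJS.

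The SAP does have a baseline-relative idea. In section 3.2.3, "New-onset symptoms will be those with a maximum severity post-infection (starting on the day of first RT-PCR positivity) above that of baseline", for infected participants. Section 7.1.2 uses it for Figure 9 only. Table 14 tests the case definition by varying the MJS cut-off (to 10, and to "Cumulative MJS ≥ 15 across Days 2 through 6, Days 3 through 7, or Days 4 through 8"), the number of shedding days and the PCR assay. No row adjusts for baseline.

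**The concern.** The first primary objective is to find a dose that produces symptomatic infection, and the attack rate is read against an absolute target of 55%-80%. Symptoms that were there before inoculation and simply persist are not produced by the dose, yet they score in full on Days 2-8. In a participant who sheds, they can supply the symptom half of the case definition. The attack rate then moves towards the shedding rate, and part of what is reported as symptomatic influenza is background.

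The documents give some reason to expect background. Inclusion criterion 10 bars "aspirin, intranasal steroids, decongestants, antihistamines, and other non-steroidal anti-inflammatory drugs" from 7 days before through confinement unless the investigator approves, and several MJS items (runny nose, stuffy nose, sneezing, headache, body ache) are symptoms that such drugs treat. Lymphopenia is a scored item, while at entry "Labs within normal range or grade 1 abnormalities deemed not clinically significant by a study investigator are considered acceptable". The sponsor also treats background as real: exploratory objective 7 is about it, and protocol section 9.3.1 justifies the shams by the wish to limit false positive symptoms.

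**Working it through.** **1. The plan's own figures.** The documents give no pre-challenge symptom rate, so there is no plan figure for this point. The nearest are the Cohort 1A operating characteristics and the precision statement. They reproduce: the probability of at least 8 cases in 10 is 0.0123 at a true rate of 0.4 (stated 0.01), 0.3828 at 0.7 (SAP 0.38) and 0.6778 at 0.8 (protocol 0.67). The exact 95% interval for 15/30 is 31.3%-68.7%, as stated. All take the case probability as given, so they do not bear on how cases arise.

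**2. What unchanged symptoms score.** Points in a window = 5 days × the sum of the constant daily item scores. Scheduled lymphocyte counts fall on Days 2, 4 and 8, so a Grade 1 result that meets the scoring limit adds 2, 1 or 2 points in windows 2-6, 3-7 and 4-8.

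| Unchanged background | Points | ≥ 6 | ≥ 10 | ≥ 15 |
|---|---|---|---|---|
| One mild item | 5 × 1 = 5 | no | no | no |
| One mild item + scored Grade 1 lymphopenia | 5 + 2 = 7 | yes | no | no |
| Two mild items, or one moderate | 5 × 2 = 10 | yes | yes | no |
| Three mild items, or one severe | 5 × 3 = 15 | yes | yes | yes |

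One constant mild item does not make a case alone; it needs one more point. Two are enough, and they survive the cut-off of 10.

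**3. Effect on the attack rate (AR).** Let q be the proportion meeting the shedding criterion, s the proportion of shedders whose challenge-caused score alone reaches 6, and b the proportion of the remaining shedders whom background brings to 6. Then AR = q × [s + (1 − s) × b], and the excess over the challenge-caused rate is q × (1 − s) × b. All three inputs are assumptions.

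| q | s | b = 0 | 5% | 10% | 20% | 30% |
|---|---|---|---|---|---|---|
| 0.80 | 0.75 | 60% | 61% | 62% | 64% | 66% |
| 0.80 | 0.60 | 48% | 49.6% | 51.2% | 54.4% | 57.6% |
| 0.60 | 0.75 | 45% | 45.75% | 46.5% | 48% | 49.5% |
| 0.60 | 0.60 | 36% | 37.2% | 38.4% | 40.8% | 43.2% |

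Example, first row at b = 30%: 0.80 × (0.75 + 0.25 × 0.30) = 0.66. The largest shift in this grid is 0.80 × 0.40 × 0.30 = 9.6 points, which takes an AR of 48% to 57.6%, across the lower edge of the 55%-80% target.

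**4. What the planned displays can show.** In Table 14, the count with MJS ≥ 6 minus the count with symptomatic infection is the number of uninfected participants who reached 6, by group. That is a background rate in other people. It does not show which cases had their symptoms beforehand. Tables 22-27 give severity item by item, and Table 43 gives score summaries. None reclassifies a case.

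**The case against.** The strongest reply is that background is already well described. Tables 22-25 show baseline and Day 1 beside post-challenge days, Table 27 tests pre-infection against current-infection severity for every item, Table 43 gives scores in uninfected participants, Listing 8 gives the item data, and Table 14 includes the sham group. This stands: a reader might infer from the narrow use of new-onset symptoms that the plan overlooks background, and it does not. What is missing is one step, an AR recalculated within participant. About 8 shams cannot supply it with useful precision.

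Eligibility also limits background. Exclusion 1b removes people with symptoms suggestive of respiratory infection in the two weeks before challenge, exclusion 14 names undiagnosed ongoing fatigue, exclusions 16 and 17 remove nasal abnormality and frequent sinusitis, and eligibility is reconfirmed through Day 1. Non-shedders cannot become cases. These points reduce the likely size but do not close the gap.

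Three stronger readings are tempting and not supported:

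- **That the drug restrictions provoke symptoms.** No section says so, nothing shows how many participants used these drugs, and exceptions are allowed. Washout is a possible contributor only.
- **That background alone makes large numbers of cases.** Random daily noise averaging 0.5, 0.75 or 1.0 points (an assumed Poisson model) takes 8%, 29% or 55% of participants to 6. That noise is not symptoms present before inoculation. Subtracting even the highest pre-challenge score would cut these figures only to 5%, 18% and 33%.
- **That a single misclassified case wrongly decided escalation, as in 9/12 = 75% against 10/12 = 83%.** SAP sections 4.1 and 5.2 say the escalation AR included the sham, and 10/13 = 77% is still below 80%. The SAP describes those decisions in the past tense, so a report-stage analysis cannot alter them.

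Finally, a future trial using the same restrictions and definition would plan on the unadjusted AR, and background similar at all doses should not normally reorder them. Both points are fair. They support keeping the primary definition; they do not show how much of the AR the inoculum caused.

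**Conclusion.** The point holds as a cheap improvement, not as a flaw in the primary analysis. The case definition uses raw post-challenge scores, the pre-challenge scores are in hand, and neither the higher cut-offs nor the descriptive tables remove a shedder with two or three constant mild symptoms from the AR. The effect cannot be sized from the documents. With 80% shedding and 75% challenge-caused symptoms in shedders, background of 5%-30% adds 1 to 6 points to an AR of 60%. With 60% challenge-caused symptoms, it adds up to 9.6 points to an AR of 48%. If few participants had persistent symptoms before challenge, the effect is close to nil, and the added row would show that.

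**What to change.** Keep the protocol definition as primary. Add to Table 14 one sensitivity AR with the same shedding rule, the same windows and the same cut-off of 6, in which each item's daily score is reduced by that participant's persistent pre-challenge score for the item, floored at 0. A suitable persistent score is the median of the three pre-challenge daily scores (Day -2, Day -1, Day 1 before challenge). The median is preferable to the maximum, because a single transient mild score would otherwise remove up to 5 points from a genuine new symptom. Apply the reduction to fever and feverishness after they are combined into one item. For lymphopenia use the screening value, with a note that it may be up to 45 days old. State the rule for a missing pre-challenge day.

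Report by dose group how many primary cases change status, and show both ARs beside the optimal-dose statement in the CSR.

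The cost is a paragraph of SAP text and a few table rows; all data are already collected. The downsides should be stated with the result. The corrected AR can only be equal or lower, pre-existing symptoms that worsen count only for the increase, and the number of cases lost is an upper guide to misclassification from persistent symptoms, not a count of it.

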3.2.6. Mild-to-Moderate Influenza Disease (MMID-2)

In addition to the symptomatic influenza infection definition used for the primary analysis, MMID-2 will be computed based on the following criteria reported at any point during the challenge period:

1. Viral shedding detected on at least two study days by any approved positive RT-PCR assay (qualitative or quantitative, as described in [Section 3.2.2](#)) from a NP swab.
2. Any one or more of the following symptoms or signs or laboratory findings, as related to the study agent: Arthralgia, Chest tightness, Chills, Conjunctivitis, Nasal Congestion, Sinus Congestion, Coryza, Decreased Appetite, Diarrhea, Dry Cough, Dyspnea/Shortness of Breath, Fatigue/Tiredness, Fever ($>38.0^{\circ}\text{C}$), Headache, Lymphopenia (<1000 cells/mL), Myalgia, Nausea, Oxygen Saturation Decrease by $\geq 3\%$ from baseline, Productive Cough, Rhinorrhea, Sore throat, and Sweats.

Fever is determined based on temperature taken as part of vital signs assessments, and lymphopenia based on the absolute lymphocyte count assessed as part of the clinical safety labs. All other items are determined via the corresponding questions on the FLU-PRO questionnaire; component questions on FLU-PRO do not all match the language above exactly, but any reported FLU-PRO symptoms result in the threshold described in #2 being met.

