On Day 1, participants are randomized and administered a single challenge dose of either a sham inoculum or a virus dose between 10^4 and 10^6 TCID₅₀. The challenge inoculum is administered using the MAD Nasal Intranasal Mucosal Atomization Device (Teleflex, Morrisville NC) attached to a 1cc syringe. Approximately 500 μ L of study product is delivered in each nostril with the participant in a recumbent position. The dosing plan follows an adaptive dose-escalation schedule (Figure 1) that includes up to 8 different challenge cohorts. This dosing plan was designed to optimize participant safety, starting with a low dose and allowing flexibility to make informed adjustments between challenge cohorts from outcome results of the previous challenge cohort. For the first exposure in humans, the initial low dose challenge is conducted in a group of a targeted total of 13 participants (including 1 sham) to assure the virus is safe with no study-related or unanticipated adverse events observed or reported before further use. Dose escalation to the next (higher) dose and subsequent higher doses, if necessary, is informed by both safety and AR outcomes given a pre-specified decision algorithm for dose-escalating.

Clinical outcomes (see below) and pre-defined halting criteria were used to determine whether the trial moves forward to the higher dose of the challenge strain.

Symptomatic influenza virus infection criteria is based on the virologic assessment and the modified Jackson score. A participant is defined as having symptomatic influenza virus infection if the following criteria are met:

- Viral shedding detected in NP swab(s) by qualitative RT-PCR on at least two days beginning 24 hours after challenge until Study Day 8.
- A cumulative symptom score ≥ 6 from daily component symptoms, including documented fever, computed across any consecutive 5-day window through Day 8 beginning on Day 2 post challenge

using a modified Jackson score. Highest point score per day per sign or symptom will be used. Component signs and symptoms include fever, lymphopenia (< 1000 cells/mL), runny nose, stuffy nose, sneezing, sore throat, headache, cough, malaise, body ache, chills, feverish, shortness of breath, and earache ranked on a 4-point severity scale (0-3). Temperature will be measured three times a day and symptoms will be collected twice daily on the modified Jackson score. A documented fever and feeling feverish will count as one point on the cumulative symptom score.

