	None	x (x.x)	-	x (x.x)	-	x (x.x)	-	x (x.x)	-
	1: Just Noticeable	x (x.x)	-	x (x.x)	-	x (x.x)	-	x (x.x)	-
	2: Bothersome from Time to Time	x (x.x)	-	x (x.x)	-	x (x.x)	-	x (x.x)	-
	3: Bothersome Most or All of the Time	x (x.x)	-	x (x.x)	-	x (x.x)	-	x (x.x)	-
Lymphopenia ^c	Any Severity	x (x.x)	(x.x, x.x)	x (x.x)	(x.x, x.x)	x (x.x)	(x.x, x.x)	x (x.x)	(x.x, x.x)

Symptom	Maximum Severity	10 ⁴ TCID ₅₀ Challenge Virus (N=X)		10 ⁵ TCID ₅₀ Challenge Virus (N=X)		10 ⁶ TCID ₅₀ Challenge Virus (N=X)		Sham Inoculum (N=X)	
		n (%)	95% CI	n (%)	95% CI	n (%)	95% CI	n (%)	95% CI
	None	x (x.x)	-	x (x.x)	-	x (x.x)	-	x (x.x)	-
	Mild	x (x.x)	-	x (x.x)	-	x (x.x)	-	x (x.x)	-
	Moderate	x (x.x)	-	x (x.x)	-	x (x.x)	-	x (x.x)	-
	Severe	x (x.x)	-	x (x.x)	-	x (x.x)	-	x (x.x)	-

Notes: N = Number of participants in the Safety population; n = Number of participants reporting each symptom.

^aAs reported on the Modified Jackson Score (MJS) tool; maximum severity across the challenge period reported.

^bAs part of vital signs assessments, with temperature collected three times daily during the challenge period. Fever and feverishness (from MJS) contribute as one item towards the Modified Jackson Score.

^cAs part of clinical safety laboratory assessments, on Study Days 2, 4, 8, and any supplemental visits during the challenge period.

Table 16: Maximum Severity of Influenza Symptoms Reported During the Challenge Period by Challenge Dose Group, Infected Participants in the Safety Population

Symptom	Maximum Severity	10 ⁴ TCID ₅₀ Challenge Virus, RT-PCR+ (N=X)		10 ⁵ TCID ₅₀ Challenge Virus, RT-PCR+ (N=X)		10 ⁶ TCID ₅₀ Challenge Virus, RT-PCR+ (N=X)		Any Active Challenge Virus Dose, RT-PCR+ (N=X)		Sham Inoculum, RT-PCR+ (N=X)	
		n (%)	95% CI	n (%)	95% CI	n (%)	95% CI	n (%)	95% CI	n (%)	95% CI
Any Symptom	Any Severity	x (x.x)	(x.x, x.x)	x (x.x)	(x.x, x.x)	x (x.x)	(x.x, x.x)	x (x.x)	(x.x, x.x)	x (x.x)	(x.x, x.x)
	None	x (x.x)	-	x (x.x)	-	x (x.x)	-	x (x.x)	-	x (x.x)	-
	Mild or Just Noticeable	x (x.x)	-	x (x.x)	-	x (x.x)	-	x (x.x)	-	x (x.x)	-
	Moderate or Bothersome from Time to Time	x (x.x)	-	x (x.x)	-	x (x.x)	-	x (x.x)	-	x (x.x)	-
	Severe or Bothersome Most or All of the Time	x (x.x)	-	x (x.x)	-	x (x.x)	-	x (x.x)	-	x (x.x)	-
Runny Nose ^a	Any Severity	x (x.x)	(x.x, x.x)	x (x.x)	(x.x, x.x)	x (x.x)	(x.x, x.x)	x (x.x)	(x.x, x.x)	x (x.x)	(x.x, x.x)
	None	x (x.x)	-	x (x.x)	-	x (x.x)	-	x (x.x)	-	x (x.x)	-
	1: Just Noticeable	x (x.x)	-	x (x.x)	-	x (x.x)	-	x (x.x)	-	x (x.x)	-

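### The primary symptom score has two unreconciled scoring rules for fever and two for lymphopenia, so case status near the threshold of 6 depends on which rule is programmed

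*SAP*

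**What the plan says.** The symptom half of the primary outcome is "A cumulative symptom score ≥ 6 from daily component symptoms, including documented fever, computed across any consecutive 5-day window through Day 8" (SAP 3.2.1). Its components are "all ranked on a 4-point severity scale (0-3").

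**Fever.** SAP 3.2.1 grades documented fever by Table 5 and says that it and feverishness "contribute once to the computation; the maximum of the two severity scores will be used to compute the MJS". SAP 4.1 says: "A documented fever and feeling feverish will count as one point on the cumulative symptom score". The note under Clinical Outcomes in protocol 4.1 carries the same sentence. Footnotes to the symptom tables in the SAP (for example Table 15) use a third wording: "Fever and feverishness (from MJS) contribute as one item towards the Modified Jackson Score".

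**Lymphopenia.** The component list in SAP 3.2.1 reads "Component signs and symptoms include fever, lymphopenia (< 1000 cells/mL), runny nose", and protocol 4.1 and SAP 4.1 print the same cut and unit. SAP 3.2.1 then adds: "Lymphopenia is determined based on clinical safety laboratory assessments at Days 2, 4, and 8, and graded according to Table 4". In Table 4 (protocol Appendix B), Grade 1 runs from 0.50 x10³/µL up to the lower limit of normal (LLN), and no LLN value is given. The MMID-2 definition in SAP 3.2.6 repeats "Lymphopenia (<1000 cells/mL").

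**Declared changes.** SAP 3.2.1 declares a single change from the protocol's case definition, the addition of quantitative RT-PCR. SAP Section 14 reports no substantive changes to the planned analysis.

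**The concern.** Fever and lymphopenia are not scored by the investigator on the MJS form. SAP 4.6.1 says they are assessed separately, and protocol 8.1.4.1 has the coordinating center calculate the score. The written rule therefore decides the points, and for both components the documents print two rules.

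The score feeds the attack rate (AR) that drove escalation and the AR that will be reported as the primary result. A participant who sheds virus on two days can be a case under one rule and not under the other. Table 14 varies the assay, the MJS cut-off (10 and 15) and the number of shedding days, but never the scoring of a component, so no planned analysis would show the effect.

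The table shells are not uniform either. Tables 15, 16 and 44 leave cells for mild, moderate and severe lymphopenia, while Tables 20, 26 and 27 print dashes in those rows.

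**Working it through.** **The plan's own figures.** The documents give no figure for the effect of the scoring rule. The nearest figures on this endpoint are P(X ≥ 8) for X ~ Binomial(10, p). These come to 0.0123 at p = 0.4, 0.3828 at p = 0.7 and 0.6778 at p = 0.8, against the stated 0.01 and 0.38 (SAP 4.4.1) and 0.67 (protocol 9.3.2). The exact 95% interval for 15/30 is 31.3% to 68.7%, as stated. These figures reproduce, but they take case status as given.

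**Inputs.**
- Threshold 6 over Days 2-6, 3-7 or 4-8 (SAP 3.2.1, Table 14).
- Fever grades 1-3 (Table 5); feverish 0-3 (MJS form, SAP Figure 4).
- Lymphocyte counts scheduled on Days 2, 4 and 8.
- Table 4: Grade 1 = 0.50 to <LLN, Grade 2 = 0.40-0.49, Grade 3 = <0.40 x10³/µL.
- Cohort 1A: 12 active plus 1 sham, 80% rule (protocol 4.1).

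**Fever.** Let m be the higher of the fever grade and feverish severity on a day. SAP 3.2.1 sums m over the window. The one-point sentence can be read as one point per day with m > 0, or as one point in the whole cumulative score.

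| Profile in one window | Daily maximum | One point a day | One point in total |
|---|---|---|---|
| Grade 2 on three days | 3 × 2 = 6 | 3 | 1 |
| Grade 3 on two days | 2 × 3 = 6 | 2 | 1 |
| Grade 2 on one day + 4 other points | 2 + 4 = 6 | 1 + 4 = 5 | 5 |
| Grade 2 on two days + 2 other points | 4 + 2 = 6 | 2 + 2 = 4 | 3 |
| Grade 1 on five days | 5 | 5 | 1 |
| Ceiling over five days | 15 | 5 | 1 |

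The first four profiles meet the threshold only under SAP 3.2.1. At Grade 1 the daily maximum and one point a day agree. They part only from Grade 2 upward, which feverishness alone can reach without a high temperature.

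**Lymphopenia, unit.** 1000 cells/mL = 1 cell/µL = 0.001 x10³/µL. The Grade 3 bound is 0.40, and 0.40 / 0.001 = 400. The printed cut is not physically plausible.

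**Lymphopenia, threshold.** Assume cells/µL was meant, so the fixed cut is 1.0 x10³/µL. It agrees with Table 4 on presence only when LLN = 1.0. The documents give no LLN, so a range is needed:
- LLN assumed 1.1 to 1.5: counts from 1.0 to <LLN score 1 under Table 4 and 0 under the fixed cut.
- LLN assumed 0.8 to 0.9: counts from LLN to <1.0 meet the fixed cut but have no grade.

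The three windows hold 2, 1 and 2 scheduled counts, so a Grade 1 disagreement moves the score by at most 2 × 1 = 2 points.

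**Effect on the AR.** SAP 4.1 counts all participants in a cohort, sham included, so one participant is 1/13 = 7.7 percentage points. For Cohort 1A, 10/13 = 76.9% falls below 80% and 11/13 = 84.6% is above it. On the 12 active participants alone the pair is 9/12 = 75.0% and 10/12 = 83.3%.

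**The case against.** The best reply is that the intended rules can be identified. SAP 3.2.1 is the derived-variables section and gives a programmable fever rule. SAP 4.1 is a design summary that points back to Section 3.2. The footnotes speak of one item, which fits the daily maximum. Protocol 4.1 itself lists fever among components scored 0 to 3 and refers to Appendix A for temperature. One point is then loose wording for not counting the pair twice. Lymphopenia is sent to Table 4, which is in x10³/µL. Listing 8 prints daily component severities, so any rescoring can be checked. For MMID-2, any reported FLU-PRO symptom already meets the criterion, so the unit slip there rarely matters.

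Most of this stands, and it is why the fix keeps the SAP 3.2.1 fever rule. It does not remove the conflict: the other fever rule is still printed in both documents, and naming Table 4 does not say whether the fixed cut or the LLN decides a Grade 1 score.

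A reader might infer three stronger things that the documents do not support:
- *Lymphopenia can never score.* It would score under Table 4, which the same section names.
- *Interim and final ARs were scored differently.* Nothing states which component rules the escalation ARs used, so this is possible but not shown.
- *The two sites score equal counts differently.* Each site uses its own clinical laboratory (protocol 8.2), but no LLN is given for either.

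**Conclusion.** The primary case definition contains two unreconciled scoring rules, and the fever difference is not declared as a change from the protocol. For fever, the same data can give 6 or 3 points against a threshold of 6. The gap over one window is at most 15 − 5 = 10 points on the one-point-a-day reading, or 15 − 1 = 14 on the single-point reading. Both are ceilings, not expected sizes. For lymphopenia, the printed unit is wrong by any plausible reading. The remaining Grade 1 conflict is worth at most 2 points, assuming cells/µL was meant and only the scheduled counts are used.

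The effect is confined to participants who meet the shedding criterion and score near 6. Their number cannot be known from the documents, and no case classification or escalation decision is shown to have changed. But one such participant is enough to move Cohort 1A across its 80% rule, and the correction is cheap, so the text should be settled before the final analysis is programmed.

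**What to change.** 1. **Fever.** Keep the SAP 3.2.1 rule: one item, scored 0 to 3, the daily maximum of fever grade and feverish severity. Put it in place of the one-point sentence in protocol 4.1 and SAP 4.1.
2. **Lymphopenia.** Correct the unit to cells/µL in protocol 4.1 and SAP 3.2.1, 3.2.6 and 4.1. State whether the cut of 1000 cells/µL or the Table 4 LLN decides if Grade 1 scores, using the rule applied for the escalation ARs.
3. **Disclosure.** State which fever and lymphopenia rules the escalation ARs used, and declare any difference from the final rules in SAP 3.2.1 and Section 14.
4. **Sensitivity.** Add one Table 14 row with the alternative component scoring.

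New fixed lymphocyte cuts at both sites are optional. If escalation used Table 4, they would create a new difference between the escalation and final ARs.

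The cost is wording in a few sections and one table row. No new data are needed.
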